The study is observational, retrospective-prospective, multicenter "real-life" study involving 26 centers belonging to the SEIFEM group. Regarding the retrospective part, clinical data will be collected on all patients with LMA FLT3+ (ITD or TKD mutation) treated with Gilteritinib from when the drug was approved and marketed in Italy (April 2, 2020) until April 30, 2022. Enrollment in the prospective cohort will have an estimated duration of 24 months from the time of study approval. Patients enrolled in the last month will be followed for six months from the date of enrollment to check for the occurrence of any infections. For each case of a patient receiving salvage monotherapy with Gilteritinib, a control patient with LMA R/R FLT3+ on salvage chemotherapy should also be included.

Study Duration.

Relative to the prospective part, the study will have a total duration of 24 months from the first patient enrolled and six months of observation from the last patient enrolled.

Population

Inclusion criteria:

- All patients with FLT3+ relapsed/refractory AML to any line of therapy treated with Gilteritinib
- Patients ≥ 18 years of age
- Signature of appropriate informed consent

Exclusion criteria:

- Patients < 18 years old

Study Objectives.

The purpose of the present retrospective/prospective study is to evaluate the "real life" incidence of infectious complications in patients with relapsed/refractory FLT3+ AML treated with Gilteritinib.

Primary objective

To assess "real-life" in patients with relapsed/refractory FLT3+ LMA treated with Gilteritinib the absolute infectious risk and compare it with relapsed/refractory patients receiving chemotherapy.

Secondary objectives.

- To assess the site, incidence and outcome of bacterial/fungal/viral infections in this patient setting
- To assess the need for hospitalization and the duration of hospitalization
- To analyze the different antifungal prophylaxis policies in different Hematology Centers and correlate them with the incidence of infection
- To analyze the incidence of side effects related to the use, in combination with Gilteritinib, of antifungal/antibacterial/antiviral drugs (in prophylaxis/therapy).

Methods

The proposed study is retrospective-prospective, multicenter, observational.

Data will be retrospectively collected from all cases observed from April 2, 2020 until April 30, 2022 about the infectious event and related treatment information (database attached).

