In the prospective cohort, enrollment will have an estimated duration of 24 months from the time of study approval. Patients enrolled in the last month will be followed for six months thereafter to check for the occurrence of any infections.

Data from patients with gilteritinib monotherapy and data from patients for whom the clinician's choice is the use of chemotherapy (consisting, for example, of the following regimens: FLA-IDA, MICE, MEC, intermediate/high-dose cytarabine) will have to be analyzed to assess the infectious risk associated with gilteritinib monotherapy.

It is reiterated that since this is an observational study, the choice of therapy is at the discretion of the treating hematologist and independent of enrollment in this study.

Informed consent will be sought from all patients still alive at the time of initiation of data collection and from patients whose data will be collected prospectively. However, it should be noted that since this is a study that mainly considers patients with relapsing hemopathies that could be complicated by life-threatening infections, the rate of obtainable consents may be reduced due to the mortality of these hemopathies.

The incidence of infection will be related to the following variables:

- Age
- Sex
- Comorbidities
- Type of antimicrobial prophylaxis performed
- Type of FLT3 mutation (ITD vs TKD)
- Type of response to treatment
- Hospitalization and duration

Any side effects related to the combination of Gilteritinib with antimicrobial drugs used in prophylaxis/therapy by different centers will also be evaluated.

The study will not affect normal care practice in any way, as there is no blood sampling for patients. Each patient and each control will be assigned an identification code that will allow the omission of any reference that would allow patient recognition.

Clinical information will pertain to the coordinating center and will be collected within a database.

Based on the following considerations:

- it is assumed that the reference population, or target population from which the sample is drawn (78 patients), is Gaussian distributed with unknown variance;
- the null hypothesis (superposibility of the two populations: sample and target) is rejected if the sample mean differs from the mean value of the reference population by an amount, in absolute value, equal to or greater than 36.7 percent of the standard deviation;

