- we adopt, for testing the hypotheses (null and alternative), the two-tailed Gauss z-test with $\alpha = 0.05$ (error of the first kind) and $\beta = 0.10$ (error of the second kind), which implies, as is well known, a test power of 90%;

at least 78 patients are expected to be enrolled.

The analysis will be aimed at evaluating the distribution of infectious events (viral/bacterial/fungal) and identifying parameters that significantly influence the outcome of infectious complication.

With regard to descriptive statistical analyses, central tendency, variability, symmetry and kurtosis will be calculated, all accompanied by appropriate graphical representations; with regard to inferential analyses, in addition to multivariate binary logistic regression, parametric and nonparametric hypothesis testing will be carried out, respectively, for quantitative variables with parametric tests such as: Student's t-test, Fisher's F-test, etc. and for categorical variables by nonparametric tests such as: chi-square, Mann Whitney's U, Fisher's exact test, etc. Only results with p-values ≤ 0.05 will be considered statistically significant.

The study does not involve any expenses related to data collection or additional examinations.

Italian Hematology Centers belonging to the SEIFEM Group, which includes both university and hospital facilities, will participate in the study (Appendix 1: list of participating centers).

Data collection and analysis and report preparation will be the responsibility of the scientific board.

Dissemination of results

Publication of results in leading international scientific journals dealing with topics related to hematology and infectious diseases. Also, presentation of results at major national and international hematology congresses, (American Society of Hematology, European Hematology Association, Italian Society of Hematology)

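### The objective relating centres' antifungal prophylaxis policies to infection has no analysis that accounts for centre, so the unadjusted chi-square and logistic p-values are too small if policy is set by centre and infection risk varies between centres

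*Combined protocol and SAP*

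**What the plan says.** The Study design section describes a "study involving 26 centers belonging to the SEIFEM group". Among the secondary objectives is this one: "To analyze the different antifungal prophylaxis policies in different Hematology Centers and correlate them with the incidence of infection".

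The Methods section lists the variables to which infection incidence will be related. Prophylaxis appears there at patient level, as "Type of antimicrobial prophylaxis performed". Centre is not on the list.

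For inference, Methods states that "in addition to multivariate binary logistic regression, parametric and nonparametric hypothesis testing will be carried out", and gives t, F, chi-square, Mann-Whitney and Fisher's exact tests as examples, with significance at p ≤ 0.05. No centre covariate, stratum, random effect, GEE, clustered variance, ICC or design effect appears anywhere.

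On size, "at least 78 patients are expected to be enrolled". Study design adds that for each gilteritinib monotherapy case "a control patient with LMA R/R FLT3+ on salvage chemotherapy should also be included". The document does not say whether the 78 includes these controls.

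**The concern.** If each centre applies its own prophylaxis policy, all its patients share the same exposure. The independent units for the policy question are then at most 26 centres, however many patients are enrolled. Patients at one centre also share diagnostics, local flora, referral pattern and case mix, so their infection outcomes are likely to be correlated. An ordinary chi-square test or logistic model ignores this and uses a variance that is too small by the design effect.

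What is at stake is a false association between a prophylaxis policy and infection, declared at p ≤ 0.05 and published, when the true error rate is above 5%.

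**Working it through.** **The plan's own figure.** The 78 comes from a two-sided one-sample z-test with α = 0.05, power 90% and a difference "equal to or greater than 36.7 percent of the standard deviation":

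n = ((1.960 + 1.282)/0.367)² = 78.01.

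The stated 78 reproduces (power at n = 78 is 0.89995). It contains no allowance for clustering. It is not in dispute here; it serves only to fix the number of patients per centre.

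**Inputs from the document.** 26 centres; N = 78, so m = 78/26 = 3 per centre on average; or N = 156, so m = 156/26 = 6, if the 78 are cases with one control each.

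**Assumptions, not in the document.** ICC 0.05, 0.10 and 0.20; centre-size coefficient of variation (CV) 0 or 0.7; policy split 13 versus 13 centres; infection risk 35%. The risk matters only for the simulations; the formula below does not use it.

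**Formula.** For an exposure constant within centre:

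- design effect DE = 1 + (m(1 + CV²) − 1) × ICC
- actual two-sided level of a nominal 5% test = 2 × (1 − Φ(1.96/√DE))

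For m = 3 and CV 0, DE = 1 + 2 × ICC. For m = 6 and CV 0, DE = 1 + 5 × ICC. For m = 3 and CV 0.7, DE = 1 + (3 × 1.49 − 1) × ICC = 1 + 3.47 × ICC. For m = 6 and CV 0.7, DE = 1 + (6 × 1.49 − 1) × ICC = 1 + 7.94 × ICC.

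| N | Centre sizes | DE at ICC 0.05 / 0.10 / 0.20 | Actual level |
|---|---|---|---|
| 78 | equal | 1.10 / 1.20 / 1.40 | 6.2% / 7.4% / 9.8% |
| 78 | CV 0.7 | 1.17 / 1.35 / 1.69 | 7.0% / 9.1% / 13.2% |
| 156 | equal | 1.25 / 1.50 / 2.00 | 8.0% / 11.0% / 16.6% |
| 156 | CV 0.7 | 1.40 / 1.79 / 2.59 | 9.7% / 14.3% / 22.3% |

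**Check by simulation** (beta-binomial centre risks, 13 versus 13 centres, Pearson chi-square without continuity correction, which is also the score test of a logistic model with policy as its only term). With 78 patients in equal centres the level was 6.3% / 7.4% / 10.1% at 35% risk (15,000 runs per setting). At 25% risk, the invasive fungal infection rate cited in the Background, it was 6.5% / 7.7% / 10.4% (20,000 runs). With 156 patients in equal centres at 25% risk it was 8.2% / 11.3% / 17.2%. Formula and simulation agree.

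**Fisher's exact test** is conservative to begin with. At 25% risk and 78 patients in equal centres it gave 3.7% / 4.8% / 6.5%. With 156 patients in equal centres it gave 5.7% / 8.5% / 13.5%.

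**A clustered alternative.** A cluster-robust score test referred to t on 24 degrees of freedom stayed between about 3% and 5% in these simulations.

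**The case against.** **The exposure may not be constant within centre.** Methods lists the prophylaxis the patient actually received, and data run from April 2020 through a 24-month prospective phase, so practice may change within a centre. This stands, and it shrinks the problem. With 35% risk, equal centres and an assumed exposure ICC of 0.3 to 0.6, the simulated level at outcome ICC 0.05 and 0.10 was 5.5–5.6% and 5.8–6.7% for 78 patients, and 6.0–6.8% and 6.8–9.1% for 156. It does not remove the problem: the objective is worded by centre policy, and individual prophylaxis that follows local policy is still clustered.

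**The list of tests is open-ended.** True: a clustered analysis is not excluded. It is not specified either, and every method that is named assumes independence.

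**A reader might infer that every named test is inflated in every setting.** That does not hold. Fisher's exact test stays below 5% for 78 patients in equal centres up to ICC 0.10.

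**A reader might also infer that the gilteritinib versus chemotherapy comparison is anti-conservative.** The documents do not support this. Therapy is the haematologist's choice and each case needs a control, so both treatments may well occur within a centre. In that case the unadjusted test is conservative: with 3 versus 3 patients per centre, its level was 4.5% / 3.9% / 3.0% at ICC 0.05 / 0.10 / 0.20. No claim is made about the primary comparison.

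**Conclusion.** The point holds for the prophylaxis-policy objective. If policy is set by centre and infection risk varies between centres, the unadjusted chi-square and logistic p-values are too small. The direction follows from any positive ICC. The size rests on assumptions: modest for 78 patients in equal centres (about 6–7% / 7–8% / 10% at ICC 0.05 / 0.10 / 0.20), and substantial for 156 patients in centres of uneven size (about 10% / 14% / 22% at CV 0.7). The last set combines several unfavourable assumptions and should be read as the upper part of the range, not as the expected result.

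This is a secondary objective in an observational study. Neither the 78-patient calculation nor the primary comparison is called into question.

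**What to change.** In the statistical part of Methods, for the prophylaxis objective:

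- State whether the exposure is the centre's policy or the patient's own prophylaxis. If both are wanted, define each.
- Replace the unadjusted tests with a logistic model that has a centre random intercept, or with GEE clustered by centre and a small-sample correction suited to 26 clusters. Fixed centre effects are not an option for a centre-level exposure, because they absorb it.
- State as a limitation that clustering corrects the error rate only. Differences between centres in case mix or diagnostics can still be mistaken for a policy effect.

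The cost is a few sentences of analysis wording and somewhat wider intervals. No further patients or visits are needed. Centre should already be known for each patient, but the database form is not shown and this should be confirmed.

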**Observational study on the incidence of infections in patients with relapsed/refractory FLT3+ acute myeloid leukemia treated with Gilteritinib
SEIFEM-GilteRInf 2022 (Gilteritinib Related Infections) Study.**

Background and study rationale

Acute myeloid leukemia (AML) patients with refractory or relapsed (R/R) disease after induction chemotherapy have a poor prognosis with standard chemotherapy [1]. The prognosis may be further aggravated by the susceptibility to infection of this category of patients often due to persistent neutropenia [2][3].

Activating mutations of FMS-like tyrosine kinase 3 (FLT3) are observed in approximately 30 percent of AML cases [4] mainly as in-frame internal tandem duplications (ITDs) within the juxtamembrane region of the protein or as missense point mutations in the tyrosine kinase domain (TKD). FLT3 is expressed in early hematopoietic stem and progenitor cells and regulates their proliferation and differentiation. In patients with AML, the presence of the FLT3 mutation negatively affects survival, both at diagnosis and upon failure of initial therapy [5].

Over the years, several FLT3 inhibitors, currently in development or approved for the treatment of AML, have been devised and vary in kinase selectivity, potency, and clinical activity.

Gilteritinib, is a novel selective tyrosine kinase inhibitor (TKI) that acts by showing greater specificity for FLT3 and higher potency than the first generation of TKIs, competitively inhibits the ATP-binding site of FLT3 receptors, leading to inhibition of receptor signaling and thus cell cycle disruption.

Its approval by the Food and Drug Administration, with indication for FLT3-positive R/R LMA (FLT3+), is based on the results of the phase 3 ADMIRAL study, which demonstrated its superiority over chemotherapy in this setting [6].

In the study, with a median follow-up of 17.8 months, median Overall Survival (OS) was significantly longer (by 3.7 months) in the Gilteritinib arm than in the salvage chemotherapy arm.

OS rates at 12, 18 and 24 months in patients receiving Gilteritinib were 37%, 27% and 20%, respectively (compared with 19%, 15% and 14% in the comparison arm).

Febrile neutropenia was the most common grade ≥ 3 adverse event in the Gilteritinib arm (45.9%), with pneumonia and septic shock the most common fatal adverse events (1.2% and 0.8% of cases, respectively) [7].

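### The variables to be related to infection incidence include no neutrophil measure, so the prophylaxis–infection association may be confounded by neutropenia present before treatment

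*Combined protocol and SAP*

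**What the plan says.** All references are to the combined protocol and SAP.

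- **Background and study rationale.** It refers to the "susceptibility to infection of this category of patients often due to persistent neutropenia". It also reports that febrile neutropenia was the most frequent grade 3 or higher adverse event on gilteritinib in the cited phase 3 study, at 45.9%.
- **Secondary objectives.** One of them is: "To analyze the different antifungal prophylaxis policies in different Hematology Centers and correlate them with the incidence of infection".
- **Methods, variables.** "The incidence of infection will be related to the following variables". Seven items follow: age, sex, comorbid conditions, kind of antimicrobial prophylaxis, FLT3 mutation class, treatment response, and hospital stay with its length. Neither neutrophil count nor neutropenia is among them.
- **Methods, allocation.** "the choice of therapy is at the discretion of the treating hematologist and independent of enrollment in this study". Methods also says that the study leaves usual care unchanged, so prophylaxis is not assigned either.
- **Methods, analysis.** The aim includes "identifying parameters that significantly influence the outcome of infectious complication". On technique, "in addition to multivariate binary logistic regression, parametric and nonparametric hypothesis testing will be carried out". No covariates are named for the regression.

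**The concern.** The rationale singles out one driver of infection, and the list of variables to be studied against infection does not contain it. Two stated aims are exposed: the secondary objective on antifungal prophylaxis, and the search for factors that influence infection.

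In unrandomised care, an omitted risk factor biases the association of a listed variable with infection if the two are linked. Prophylaxis is the listed variable for which such a link is most plausible. If it is used more in patients who start treatment neutropenic, prophylaxis that works could look weak, useless or harmful, because it partly marks the patients at higher risk. None of the seven items measures neutropenia directly. Treatment response and hospital stay arise after treatment starts, so they cannot stand in for a baseline value.

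**Working it through.** **The plan's own figure.** The sample size rests on a two-sided one-sample z-test with alpha 0.05, power 90% and a difference of 0.367 SD: n = ((1.960 + 1.282)/0.367)² = 78.01. This reproduces the stated 78. The point does not depend on that figure, but 78 is used below to count events.

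**Size of the possible bias.** The documents give no neutrophil distribution, no prophylaxis use by neutrophil status and no effect sizes. All inputs here are therefore assumptions:
- 60% of patients are neutropenic at treatment start.
- Infection risk is 25% with neither neutropenia nor prophylaxis (odds 0.25/0.75 = 0.333).
- The true prophylaxis odds ratio (OR) is 0.50 within each neutropenia stratum.

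One case in full: neutropenia OR 3, with prophylaxis used in 80% of neutropenic and 40% of other patients.
- Risks from odds/(1 + odds): neutropenic without prophylaxis 1.0/2.0 = 0.500; neutropenic with prophylaxis 0.5/1.5 = 0.333; not neutropenic with prophylaxis 0.167/1.167 = 0.143; neither 0.250.
- Neutropenic share among users: 0.6×0.8/(0.6×0.8 + 0.4×0.4) = 0.75. Among non-users: 0.6×0.2/(0.6×0.2 + 0.4×0.6) = 0.333.
- Risk in users: 0.75×0.333 + 0.25×0.143 = 0.286. Risk in non-users: 0.333×0.500 + 0.667×0.250 = 0.333.
- Unadjusted OR: (0.286/0.714)/(0.333/0.667) = 0.40/0.50 = 0.80.

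The same steps for other assumptions:

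| Neutropenia OR | Use: neutropenic / other | Risk: users / non-users (true OR 0.50) | Apparent OR if true OR is 0.50 | Apparent OR if true OR is 1.00 |
|---|---|---|---|---|
| 3 | 70% / 70% | 25.7% / 40.0% | 0.52 | 1.00 |
| 2 | 70% / 50% | 21.5% / 32.1% | 0.58 | 1.15 |
| 3 | 70% / 60% | 26.4% / 38.2% | 0.58 | 1.12 |
| 3 | 80% / 40% | 28.6% / 33.3% | 0.80 | 1.56 |
| 3 | 90% / 40% | 29.0% / 30.0% | 0.95 | 1.85 |
| 4 | 90% / 40% | 34.1% / 31.4% | 1.13 | 2.16 |

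The first row has no link between neutropenia and prophylaxis, hence no confounding. The small shift from 0.50 to 0.52 is non-collapsibility of the odds ratio.

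A second set of assumptions gives a similar picture: 20% risk with neither factor, neutropenia OR 2 to 5, and neutropenia in 60–80% of prophylaxis users against 30–40% of the others. A true 0.50 then appears as 0.58 to 1.11, and a true 1.00 as 1.15 to 2.12.

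**Room in the model.** The Background cites 25% for invasive fungal infection on gilteritinib and 45.9% for febrile neutropenia. Neither is the study's own endpoint; both are borrowed as assumed infection rates.
- Events in 78 patients: 78×0.25 = 19.5 to 78×0.459 = 35.8, so about 20 to 36.
- Events per variable, at one parameter each: 2.8 to 5.1 with seven variables, 2.4 to 4.5 with eight.
- If the 78 were gilteritinib patients only, with one control each, 156 patients would give 39 to 72 events: 5.6 to 10.2 per variable with seven, 4.9 to 9.0 with eight.

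**The case against.** Much of the opposing case is fair.

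- **The link is not documented.** Nothing in the documents says that prophylaxis follows neutrophil status. What they discuss for azoles is CYP3A4 interaction and toxicity monitoring. The objective is framed around policies that differ between centers, and to that extent patient-level indication matters less. This stands as a limit on size. It does not remove the point, because Methods also lists the prophylaxis each patient received.
- **The illustration is stylised.** It treats prophylaxis as given or not, whereas the list refers to its type. The apparent reversal needs both a fourfold neutropenia effect and 90% against 40% use; a 70% against 60% gap gives only 0.58. This stands.
- **The list may not be exclusive, and the data may exist.** The text does not say that only these variables will be used, and the attached database is not reproduced. This stands: what can be shown is that no neutrophil measure is named for analysis.
- **The 45.9% figure is an on-treatment event.** It says nothing about imbalance at treatment start. This stands, and the figure carries no weight in the bias argument.
- **There are too few events for another term.** This is true if a term is simply added, and it shapes the fix.

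A reader might infer that the protocol names neutropenia as the cause of infection; its wording is only that susceptibility is often due to it. A reader might also infer that FLT3 class or comorbidities would absorb a neutropenia effect. The documents give neither a mechanism nor a figure for that, and it is not claimed here.

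**Conclusion.** The point holds in a limited form. The plan's stated analysis variables leave out a risk factor that its own rationale stresses. Because care is not randomised, the patient-level association between prophylaxis and infection may therefore be confounded by baseline neutropenia. It would be too strong to say that the results are confounded, since that requires a link the documents neither state nor exclude.

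The size is unknown. On the assumed inputs, a true odds ratio of 0.50 could appear as about 0.58 with a weak link and 1.13 with a strong one; with no link there is no confounding. The consequence falls mainly on a secondary objective and on the risk-factor analysis. The change is worth making because it is cheap, and because fixing the covariate in advance avoids choosing it after the data are seen.

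**What to change.** 1. Add to the list in Methods the neutrophil count at the start of the index treatment, defined as the last routine value before the first dose and preferably analysed as continuous.
2. Prespecify it as a covariate in the logistic models relating prophylaxis to infection and in the gilteritinib–chemotherapy comparison, where treatment is also the clinician's choice.
3. Do not adjust the treatment comparison for neutropenia arising on treatment, because it may be part of the treatment effect. Report it descriptively by group.
4. In these models, let the count take the place of one post-baseline listed item (treatment response, or hospital stay and its length). Name that item before the data are analysed. The number of terms then stays at seven.
5. Report how many baseline counts are missing, separately for the retrospective and prospective cohorts.

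The cost is one extra chart value per patient, with no added sampling, and one model term. Some missing values are likely in the retrospective cohort. If the attached database already holds the count, only the analysis text changes.

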In view of recent approval (FDA 2018, EMA 2019), there is a lack of real-life experience in the literature on the management and outcome of infectious issues, which could be significant given the frailty of the patients for whom Gilteritinib is intended.

We also know that Gilteritinib is mainly metabolized through CYP3A4, so there is a recommendation in the data sheet to avoid concomitant use of strong CYP3A4 inducers. The phase I/II CHRYSALIS study [8], which evaluated potential interactions between Gilteritinib and moderate and strong CYP3A4 inhibitors (e.g., some antifungals such as fluconazole, voriconazole, and posaconazole and some antibiotics such as clarithromycin, erythromycin, and azithromycin), demonstrated a less than 2-fold increase in exposure to Gilteritinib with concomitant administration of a strong CYP3A4 inhibitor. However, this increase was not considered

clinically significant because the incidence of AEs did not differ in the two groups.

In a drug-drug interaction study, the effects of moderate CYP3A4 inhibitors (e.g., fluconazole) and strong CYP3A4 inhibitors (e.g., itraconazole) on the pharmacokinetics of Gilteritinib were evaluated.

The results showed that itraconazole was associated with a significant increase in systemic exposure of Gilteritinib (~2.3-fold), while fluconazole was associated with a smaller increase (~1.43-fold) [9]. However, in the ADMIRAL study, the use of posaconazole, itraconazole, and voriconazole was not allowed, and thus the experience of administering these drugs together with Gilteritinib is currently limited [10].

It can be seen from the data sheet that dose reduction of Gilteritinib in case of prophylaxis with azoles is not recommended, but close monitoring of Gilteritinib-related toxicity is recommended [11].

At present, experiences analyzing the incidence of invasive fungal infections in patients on Gilteritinib (25%) [12], whether prophylactically treated or not, are rare.

In light of this evidence, it also becomes essential to evaluate the incidence of side effects related to the use of antibiotic/antifungal/antiviral drugs in the prophylaxis and treatment of infections in the setting of relapsed/refractory patients undergoing continuous therapy such as Gilteritinib.

Study design

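### Prophylaxis exposure has no time definition, and the named per-patient methods cannot handle late starts, so its association with infection can be biased in either direction

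*Combined protocol and SAP*

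**What the plan says.** Under Methods, the sentence "The incidence of infection will be related to the following variables" introduces a list with age, sex, comorbidities, FLT3 mutation type, response and hospitalization. One entry is "Type of antimicrobial prophylaxis performed". It has no start date, stop date, switching rule or window, and no requirement that prophylaxis come before the infection.

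The statistical paragraph of Methods says that "in addition to multivariate binary logistic regression, parametric and nonparametric hypothesis testing will be carried out", and "for categorical variables by nonparametric tests such as: chi-square, Mann Whitney's U, Fisher's exact test, etc". No person-time, landmark, time-updated or competing-risk method is named.

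One of the four secondary objectives is "To analyze the different antifungal prophylaxis policies in different Hematology Centers and correlate them with the incidence of infection". On observation time, Methods says: "Patients enrolled in the last month will be followed for six months thereafter to check for the occurrence of any infections". The Background speaks of "relapsed/refractory patients undergoing continuous therapy such as Gilteritinib".

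**The concern.** Observation lasts months, care is at the clinician's discretion, and part of the data is retrospective. Nothing in the plan anchors prophylaxis to treatment start. A label for what was performed can therefore be filled in by looking back over the whole course.

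Suppose a patient would have started on day 30 but is infected on day 10. If only starts before infection count, that patient is recorded as unexposed with an event. A similar patient who reaches day 30 uninfected is recorded as exposed. Early infections are thus sorted into the unexposed group by the coding alone. If a start after infection also counts, and infection prompts some starts, events move into the exposed group instead. Neither effect needs confounding by indication; both arise even if prophylaxis is allocated at random.

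At stake is the patient-level estimate linking prophylaxis to infection. Centers could also code the variable differently, because the plan gives no rule.

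**Working it through.** **The plan's own figure.** The stated N is a one-sample two-sided z-test: ((1.960 + 1.2816)/0.367)² = 78.01, against 78 stated. It is reproduced, and exposure coding does not affect it.

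**Inputs for the illustration**
- From the Background: 12-month survival on gilteritinib of 37%. If exponential (assumption), the death hazard is μ = −ln(0.37)/12 = 0.0829 per month, or 0.00272 per day.
- Assumed: true prophylaxis effect nil; infection risk without deaths p = 30%, 50% or 70% at day 180, constant hazard λ = −ln(1 − p)/180; share a on prophylaxis at day 0; share b starting at a uniform time in 0 to W days if still alive and uninfected; share c = 1 − a − b never starting.

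**Formula.** Let h = λ + μ.
- A planned late starter has an event before starting with probability A = 1 − (1 − e^(−hW))/(hW). This splits into infection q = (λ/h)A and death d = (μ/h)A.
- Cumulative infection is I = (λ/h)(1 − e^(−180h)).
- Exposed: total a + b(1 − q − d), infected aI + b(I − q).
- Unexposed: total c + b(q + d), infected cI + bq.

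**Worked case** (a = 0.4, b = 0.3, W = 60, p = 50%)
- Without deaths: q = 0.1071. Exposed odds 0.3179/0.3500 = 0.908; unexposed odds 0.1821/0.1500 = 1.214; OR = 0.75.
- With deaths: q = 0.1017, d = 0.0719, I = 0.4064. Exposed odds 0.25396/0.39395 = 0.6447; unexposed odds 0.15244/0.19965 = 0.7635; OR = 0.84.

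**Null ORs over p = 30% to 70%, counting only starts before infection**

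| Start pattern (assumed) | No deaths | With deaths |
|---|---|---|
| All users at day 0 | 1.00 | 1.00 |
| 60% at day 0, 20% within 14 days | 0.92–0.95 | 0.96 (0.96–0.97 by simulation) |
| 40% at day 0, 30% within 14 days | 0.91–0.94 | 0.95–0.96 |
| 40% at day 0, 30% within 60 days | 0.71–0.77 | 0.84–0.85 |
| None at day 0, 60% within 60 days | 0.54–0.63 | 0.73–0.74 |

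For the two 60-day patterns without deaths, at 30–50% risk, simulated rejection by a nominal 5% chi-square test is 8–21% at n = 78 and 11–37% at n = 156 (78 patients plus 78 controls). For the 14-day patterns it is about 5–6%.

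**The opposite direction.** Let half be on prophylaxis at day 0, and let 30% of the infected patients without it start afterwards and be counted as exposed. Then OR = [(0.5p + 0.15p)/(0.5(1 − p))] ÷ [0.35p/(0.5(1 − p))] = 0.65/0.35 = 1.86 at any p. If starts are merely planned and not prompted by infection, counting them regardless of infection gives about 1.0 without deaths. A simulation with deaths gave 1.02 to 1.39 (60% intended users, late starts within one to three months, infection risk 25% or 45.9%), because patients who die early never start.

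**Check of the remedy.** Under the null, classification by day-1 status gives both groups the same risk, so OR = 1.00. Splitting events and person-time at the start date gave simulated rate ratios of 0.99 to 1.01, with or without deaths.

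**The case against.** The strongest reply is that the plan does not commit to a biased coding. It lists a variable name only. That name could be coded as prophylaxis at treatment start, and then no immortal time exists. No section says that prophylaxis starts late; the phrase about continuous therapy describes gilteritinib. The database said to be attached is not in the available text and may already hold dates. The test list ends in an open et cetera. All this stands, so the point is a missing definition together with methods that cannot absorb late starts, and the bias is conditional.

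Three further limits also stand. The simulated contrast is ever versus never, whereas the plan names the type of prophylaxis; a type-against-type comparison is affected only if types differ in start timing or are switched. A contrast of center policies does not sort patients by when they started, so this mechanism does not reach it. Short delays and deaths both shrink the bias.

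The reply does not remove the gap. The logistic and chi-square analyses as named have no place for exposure timing, and a reader cannot tell from the plan which coding will be used.

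**Conclusion.** The point holds as a conditional one. Prophylaxis exposure is undefined in time, and the named per-patient methods would give a biased patient-level association if prophylaxis starts, switches or stops after treatment begins. Direction depends on the coding rule. Size runs from negligible (null OR 0.92–0.97 for the 60%/20% pattern within 14 days) to material (0.71–0.77 without deaths and about 0.85 with deaths for the 40%/30% pattern within 60 days). The extreme pattern, with nobody on prophylaxis at day 0, gives 0.54–0.63 and 0.73–0.74; nothing in the documents suggests it applies. Every start pattern, infection risk and the exponential death model is an assumption.

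A reader might infer more: that the plan fixes one value over the whole follow-up, that logistic regression credits waiting time to prophylaxis, or that an ineffective regimen will look protective. The documents do not support this. Fixed coding is only an inference from the methods, logistic regression uses no person-time (the mechanism is misclassification), and late starts are not documented. The center-policy objective is not undermined by this mechanism. The primary objective and N = 78 are untouched. This is a cheap improvement.

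**What to change.** 1. In the Methods list of variables, define the entry used in the logistic model and univariate tests as the type of antimicrobial prophylaxis in use on day 1 of gilteritinib or salvage chemotherapy.
2. In the statistical paragraph of Methods, add one time-to-first-infection analysis with prophylaxis as a time-updated exposure built from start and stop dates, for example a cause-specific Cox or Poisson model with death as a competing event.
3. State that prophylaxis begun after an infection does not count as exposure for that infection.

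The cost is a few lines of text, plus abstraction of start and stop dates if the attached database lacks them; their availability for retrospective cases should be checked. The day-1 definition leaves later starters in their day-1 class and so dilutes a true effect, which is why the time-updated analysis should accompany it. The sample size does not change.
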